7.4.2.2 Progress Report and Data Analysis

Information obtained during the previous year's clinical and non-clinical investigations, including:

- a narrative or tabular summary showing the most frequent and most serious adverse experiences by body system
- a summary of all serious adverse events submitted during the past year
- a summary of serious adverse events that were expected or considered to have causes not associated with the use of the gene transfer product such as disease progression or concurrent medications
- if any deaths have occurred, the number of participants who died during participation in the investigation and causes of death
- a brief description of any information obtained that is pertinent to an understanding of the gene transfer product's actions, including, for example, information about dose-response, information from controlled trials, and information about bioavailability.

7.5 NIH REQUIRED DATA AND SAFETY MONITORING PLAN

7.5.1 Principal Investigator/Research Team

The Principal Investigator, lead associate investigator and the research nurse will meet weekly at each clinic to review all adverse events for each subject in this trial. Unexpected adverse events and/or serious adverse events will be reported to the NIH Intramural Institutional Review Board (IRB) and sponsor/FDA as outlined above. If trends are noted and/or risks warrant it, accrual will be interrupted, dose levels expanded and/or the protocol and/or consent will be modified accordingly.

All data will be collected in a timely manner and reviewed by the principal investigator or a lead associate investigator. Events meeting requirements for expedited reporting as described in section **7.2.1** will be submitted within the appropriate timelines.

The principal investigator will review adverse event and response data on each participant to ensure safety and data accuracy. The principal investigator will personally conduct or supervise the investigation and provide appropriate delegation of responsibilities to other members of the research staff.

8 SPONSOR PROTOCOL/SAFETY REPORTING

8.1 DEFINITIONS

8.1.1 Adverse Event

Any untoward medical occurrence in a patient or clinical investigation subject administered a pharmaceutical product and which does not necessarily have a causal relationship with this treatment. An adverse event (AE) can therefore be any unfavorable and unintended sign (including an abnormal laboratory finding), symptom, or disease temporally associated with the use of a medicinal (investigational) product, whether or not related to the medicinal (investigational) product (ICH E6 (R2)).

8.1.2 Serious Adverse Event (SAE)

An adverse event or suspected adverse reaction is considered serious if in the view of the investigator or the sponsor, it results in any of the following:

- Death,
- A life-threatening adverse event (see **8.1.3**)
- Inpatient hospitalization or prolongation of existing hospitalization
 - A hospitalization/admission that is pre-planned (i.e., elective or scheduled surgery arranged prior to the start of the study), a planned hospitalization for pre-existing condition, or a procedure required by the protocol, without a serious deterioration in health, is not considered a serious adverse event.
 - A hospitalization/admission that is solely driven by non-medical reasons (e.g., hospitalization for patient or research subject convenience) is not considered a serious adverse event.
 - Emergency room visits or stays in observation units that do not result in admission to the hospital would not be considered a serious adverse event. The reason for seeking medical care should be evaluated for meeting one of the other serious criteria.
- Persistent or significant incapacity or substantial disruption of the ability to conduct normal life functions
- A congenital anomaly/birth defect.
- Important medical events that may not result in death, be life-threatening, or require hospitalization may be considered a serious adverse drug experience when, based upon appropriate medical judgment, they may jeopardize the patient or subject and may require medical or surgical intervention to prevent one of the outcomes listed in this definition.

8.1.3 Life-threatening

An adverse event or suspected adverse reaction is considered "life-threatening" if, in the view of either the investigator or sponsor, its occurrence places the patient or subject at immediate risk of death. It does not include an adverse event or suspected adverse reaction that, had it occurred in a more severe form, might have caused death. (21CFR312.32)

8.1.4 Severity

The severity of each Adverse Event will be assessed utilizing the CTCAE version 4.0.

8.1.5 Relationship to Study Product

All AEs will have their relationship to study product assessed using the terms: related or not related.

- Related – There is a reasonable possibility that the study product caused the adverse event. Reasonable possibility means that there is evidence to suggest a causal relationship between the study product and the adverse event.
- Not Related – There is not a reasonable possibility that the administration of the study product caused the event.

8.1.6 Adverse Events of Special Interest

Adverse events of special interest (AESIs) are serious or nonserious AEs that are of clinical interest and should be closely followed.

AESIs include the following:

- Infusion-related reactions including immediate hypersensitivity
- Immune-related adverse events
- TGF β inhibition mediated skin reactions
- Anemia
- Bleeding AEs

8.2 ASSESSMENT OF SAFETY EVENTS

AE information collected will include event description, date of onset, assessment of severity and relationship to study product and alternate etiology (if not related to study product), date of resolution of the event, seriousness and outcome. The assessment of severity and relationship to the study product will be done only by those with the training and authority to make a diagnosis and listed on the Form FDA 1572 as the site principal investigator or sub-investigator. AEs occurring during the collection and reporting period will be documented appropriately regardless of relationship. AEs will be followed through resolution.

SAEs will be:

- Assessed for severity and relationship to study product and alternate etiology (if not related to study product) by a licensed study physician listed on the Form FDA 1572 as the site principal investigator or sub-investigator.
- Recorded on the appropriate SAE report form, the medical record and captured in the clinical database.

- Followed through resolution by a licensed study physician listed on the Form FDA 1572 as the site principal investigator or sub-investigator.

For timeframe of recording adverse events, please refer to section **6.1**. All serious adverse events recorded from the time of first investigational product administration must be reported to the sponsor with the exception of any listed in section **8.4**.

8.3 REPORTING OF SERIOUS ADVERSE EVENTS

Any AE that meets protocol-defined serious criteria or meets the definition of Adverse Event of Special Interest that require expedited reporting must be submitted immediately (within 24 hours of awareness) to OSRO Safety using the CCR SAE report form. Any exceptions to the expedited reporting requirements are found in section **8.4**.

All SAE reporting must include the elements described in **8.2**.

SAE reports will be submitted to the Center for Cancer Research (CCR) at: [contact] and to the CCR PI and study coordinator. CCR SAE report form and instructions can be found at: <https://ccrod.cancer.gov/confluence/display/CCRCRO/Forms+and+Instructions>

Following the assessment of the SAE by OSRO, other supporting documentation of the event may be requested by the OSRO Safety and should be provided as soon as possible.

8.4 WAIVER OF EXPEDITED REPORTING To CCR

As death due to disease progression is part of the study objectives, and captured as an endpoint in this study, it will not be reported in expedited manner to the sponsor. However, if there is evidence suggesting a causal relationship between the study drug and the event, report the event in an expedited manner according to section **8.3**.

8.5 SAFETY REPORTING CRITERIA TO THE PHARMACEUTICAL COLLABORATORS

All events listed below must be reported in the defined timelines to [contact]. OSRO Safety will send all reports to the manufacturers as described below.

8.5.1 Reporting to [REDACTED] Research and Development Institute, Inc.

- Adverse events (AEs) which are considered Suspected, Unexpected Serious Adverse Events (SUSARs) will be reported as soon as they have been reported to the FDA in the same format (MedWatch 3500A or Council for International Organizations of Medical Services [CIOMS report]).
- A copy of the FDA IND annual report or any other safety reports requested by the FDA.

Adverse event reports will be sent to [REDACTED] electronically at the following addresses (include as applicable-protocol number, subject number, site number/PI name and SAE/Onset date):

[REDACTED]
[REDACTED]
[REDACTED]

2. [REDACTED]

[REDACTED]

[REDACTED]

[REDACTED]

[REDACTED]

8.5.2 Reporting to [REDACTED].

The sponsor should also submit all safety reports that are sent to the FDA using the Medwatch 3500 Form (or equivalent) to:

[REDACTED]

[REDACTED]

[REDACTED]

8.6 REPORTING PREGNANCY

All required pregnancy reports/follow-up to OSRO will be submitted to: [contact] and to the CCR PI and study coordinator. Forms and instructions can be found here:

<https://ccrod.cancer.gov/confluence/display/CCRCRO/Forms+and+Instructions>

8.6.1 Paternal Exposure

Male participants should refrain from fathering a child or donating sperm during the study and for four months after the last dose of the investigational immunotherapy agent. Pregnancy of the participant's partner is not considered to be an AE. The outcome of all pregnancies occurring from the date of the first dose until four months after the last dose should, if possible, be followed up and documented. Pregnant partners may be offered the opportunity to participate in an institutional pregnancy registry protocol (e.g., the NIH IRP pregnancy registry study) to provide data about the outcome of the pregnancy for safety reporting purposes.

8.7 REGULATORY REPORTING FOR STUDIES CONDUCTED UNDER CCR-SPONSORED IND

Following notification from the investigator, CCR, the IND sponsor, will report any suspected adverse reaction that is both serious and unexpected. CCR will report an AE as a suspected adverse reaction only if there is evidence to suggest a causal relationship between the study product and the adverse event. CCR will notify FDA and all participating investigators (i.e., all investigators to whom the sponsor is providing drug under its INDs or under any investigator's IND) in an IND safety report of potential serious risks from clinical trials or any other source, as soon as possible, in accordance to 21 CFR Part 312.32.

All serious events will be reported to the FDA at least annually in a summary format.

8.8 SPONSOR PROTOCOL DEVIATION REPORTING

A Protocol Deviation is defined as any non-compliance with the clinical trial Protocol, Manual of Operational Procedures (MOP) and other Sponsor approved study related documents, GCP, or protocol-specific procedural requirements on the part of the participant, the Investigator, or the

study site staff inclusive of site personnel performing procedures or providing services in support of the clinical trial.

It is the responsibility of the study Staff to document any protocol deviation identified by the Staff or the site Monitor in the CCR Protocol Deviation Tracking System (PDTs) online application. The entries into the PDTs online application should be timely, complete, and maintained per CCR PDTs user requirements.

In addition, any deviation to the protocol should be documented in the participant's source records and reported to the reviewing IRB per their guidelines. OSRO required protocol deviation reporting is consistent with E6(R2) GCP: Integrated Addendum to ICH E6(R1): 4.5 Compliance with Protocol; 5.18.3 (a), and 5.20 Noncompliance; and ICH E3 16.2.2 Protocol deviations.

9 CLINICAL MONITORING

Clinical site monitoring is conducted to ensure:

- that the rights of the participants are protected;
- that the study is implemented per the approved protocol, Good Clinical Practice and standard operating procedures; and,
- the quality and integrity of study data and data collection methods are maintained.

Monitoring for this study will be performed by NCI CCR Office of Sponsor and Regulatory Oversight (OSRO) Sponsor and Regulatory Oversight Support (SROS) Services contractor. Clinical site monitoring activities will be based on OSRO standards, FDA Guidance E6(R2) Good Clinical Practice: Integrated Addendum to ICH E6(R1) March 2018, and applicable regulatory requirements.

Details of clinical site monitoring will be documented in a Clinical Monitoring Plan (CMP) developed by OSRO. CMPs will be protocol-specific, risk-based and tailored to address human subject protections and integrity of the study data. OSRO will determine the intensity and frequency of monitoring based on several factors, including study type, phase, risk, complexity, expected enrollment rate, and any unique attributes of the study and the site. The Sponsor will conduct a periodic review of the CMP to confirm the plan's continued appropriateness. A change to the protocol, significant or pervasive non-compliance with GCP, or the protocol may trigger CMP updates.

OSRO SROS Monitoring visits and related activities will be conducted throughout the life cycle of each protocol. The first activity is before the study starts to conduct a Site Assessment Visit (SAV) (as warranted), followed by a Site Initiation Visit (SIV), Interim Monitoring Visit(s) (IMVs), and a study Close-Out Visit (COV).

Some monitoring activities may be performed remotely, while others will occur at the study site(s). Monitoring visit reports will describe visit activities, observations, and associated action items or follow-up required for resolution of any issues, discrepancies, or deviations. Monitoring reports will be distributed to the study PI, NCI CCR QA, CCR Protocol Support Office, coordinating center (if applicable), and the Sponsor regulatory file.

The site Monitor will inform the study team of any deviations observed during monitoring visits. If unresolved, the Monitor will request that the site Staff enter the deviations in the CCR

Protocol Deviation Tracking System (PDTs) for deviation reporting to the Sponsor and as applicable per institutional and IRB guidance.

10 STATISTICAL CONSIDERATIONS

10.1 STUDY OBJECTIVES

10.1.1 Primary

The primary objective is to determine if the combination immunotherapy can result in a confirmed 30% decline in PSA in a modest fraction of participants enrolled

10.1.2 Secondary

The secondary objectives are to:

- Assess the safety of the combination immunotherapy regimen
- Test for changes in PSA kinetics after treatment with the combination immunotherapy, relative to baseline PSA kinetics

10.2 SAMPLE SIZE DETERMINATION

The trial will begin with a 6-participant safety lead-in. Following determination of safety, the primary objective of this study is to determine if the use of two vaccines combined with an immune checkpoint inhibitor can be associated with a modestly high fraction of participants who can experience at least a 30% decline from their maximum PSA anytime during treatment to the minimum value during treatment.

Safety data for the 6-participant lead-in will be shared with IRB before accrual commences in the biochemical recurrence cohort. Beyond safety, this cohort will just be evaluated in a descriptive manner.

Because participants may be receiving the proposed treatment and be followed for PSA changes over an extended period, and the evaluation of the endpoint may take place at any point during this potentially long period, the trial will use a single stage design for evaluating efficacy. With 25 evaluable participants who do not receive M7824, there would be 82% power to rule out 15% and be consistent with 35% who may be able to experience a 30% decline in PSA, using an exact binomial test with a 0.10 one-sided significance level. As an illustration, if 25 evaluable participants are enrolled, 7 of 25 (28.0%) who experience at least a 30% PSA change from the maximum level would have an associated one-sided lower 90% confidence interval bound of 16.3%, and simultaneously an associated one-sided upper 90% confidence interval bound of 42.6%. These demonstrate that 7/25 would be a desirable result based on the parameters selected.

With the amendment v7/29/2021, the initial 6 participants who received M7824 will be evaluated separately in exploratory fashion and will not be included among the 25 main participants.

In addition, because a trial of participants with similar eligibility (16-C-0035) may result in approximately 36 participants who are undergoing surveillance for 6 months, this other trial may serve as a control for a secondary evaluation. The changes in PSA on this trial during the initial 6 months can be compared to the changes in PSA during the initial 6 months on the surveillance arm of the control trial as a secondary evaluation. With 25 evaluable participants on this trial and 36 evaluable participants on the other trial, there would be 81% power to identify a difference between 35% of participants on this trial with a 30% PSA maximum change and 10% of participants on the

control trial with a 30% PSA maximum change with a 0.10 one-sided significance level Fisher's exact test.

It is anticipated that 1-2 participants per month can be enrolled onto this trial; thus, it is expected that accrual of 37 evaluable participants (6 for the lead-in, 6 who received M7824 as part of the initial investigation for PSA response and 25 homogeneously treated participants to evaluate PSA response) can be completed within 1 to 2 years. To allow for a small number of inevaluable participants, the accrual ceiling will be set at 40 participants.

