2.3.1 Treatment Assignment Procedures (for registration purposes only)

Cohorts

Number	Name	Description
1	Lead-In Cohort (closed December 2018)	Participants with advanced castration resistant prostate cancer (first six participants)
2	Biochemical Recurrence Cohort	Participants with biochemically recurrent prostate cancer

Arms

Number	Name	Description
1	Combination therapy (closed December 2018)	Prostvac + CV301 + MSB0011359C
2	Combination therapy + surveillance (closed)	Surveillance followed by Prostvac + CV301 then Prostvac + CV301 + MSB0011359C
3	Combination vaccine therapy +/- surveillance	Surveillance as needed followed by Prostvac + CV301

Arm Assignment

Participants in cohort 1 will be directly assigned to Arm 1 of the study. This cohort has been closed as of December 2018.

Participants in cohort 2 will be directly assigned to Arm 2, or Arm 3 of the study based upon time of enrollment. Participants enrolling after approval of amendment dated 7/29/2021 are assigned to Arm 3.

Please note: As of December 21, 2018, the 6 participants in the lead in cohort have completed the 6-week toxicity assessment period and no SAEs were seen. Per the protocol design participants will now be enrolled to the BCR cohort. The toxicity assessment of participants in the lead-in cohort is described in section [1.2.13](#).

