begin C1D1 with vaccine therapy. In this case, the 3 PSA values obtained prior to enrollment will be evaluated as if they were collected during the surveillance period while enrolled and will factor into the determination of the intra-study apex value (See Section 6.3.2) highest PSA that is within 10% of another peak PSA for the participant on-study. Any other peak PSA values that are beyond 10% of other PSA values on the study will be determined as potential lab variability and excluded from response assessment.

- With Amendment v05/10/2023, participants that have at least 3 PSA measurements in the surveillance period, with at least one of them sufficient to provide the doubling time from baseline, will not undergo any further PSA measurements in the surveillance period.

Prostvac will be administered nearly identical to the Phase III dosing with Prostvac-V given day 1 (week 1) followed by Prostvac-F on weeks 3 and 5 then monthly for an additional 5 months. Therefore, Prostvac-V is given one time (priming vaccine) followed by 7 doses of Prostvac-F (booster vaccine). The administration schema for CV301 is representative of the Phase I dose escalation trial. MVA-BN-CV301 (priming vaccine) is administered on day 1 (week 1) and week 3 followed by FPV-CV301 (booster vaccine) administered on week 5 then monthly for an additional 5 months.

MSB0011359C (anti-PDL1 TGF β Trap) will be administered at the recommended phase II dose of 1200mg by IV infusion every 2 weeks for 3 months (6 doses) starting after 4 months of concurrent Prostvac and CV301.

Effective with amendment v7/29/2021, MSB0011359C will no longer be given as part of the treatment combination for the Biochemical Recurrence cohort (Arms 2 and 3). This cohort will now receive Prostvac and CV301 during months 1-7 following surveillance.

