10.4.2 Analysis of the primary efficacy endpoints

The fraction of evaluable participants who experience at least a 30% decline from the maximum to the minimum PSA value while on study will be determined. A two-tailed 80% and 95% confidence interval will be formed around the fraction of participants with 30% decline to interpret the fraction who experience a decline of that magnitude. This primary analysis will not include the 6 patients who received M7824 before it was removed from future use in this study.

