10.4.9 Exploratory analyses

The study will aim to evaluate immune changes after treatment with 2 vaccines for 4 months.

Many immune parameters (See Section **5.1**) will be obtained at baseline and at several time points beginning at the time the two vaccines are first administered. The changes in the immune parameters after treatment with 2 vaccines for 4 months will be determined and tested for statistical significance using a two-tailed 0.05 significance level paired t-test or Wilcoxon signed rank test (if the paired differences are not normally distributed). Since there are potentially a moderately large number of these tests, they will be reported as being of secondary intent and presented without adjustment for multiple comparisons but in the context of the number of such tests performed.

Willing participants will continue to be followed after cycle 7 until progression or ADT is clinically indicated.

Patients in cohort 2 who received M7824 as part of their therapy will have their PSA response evaluated in a descriptive fashion, and may be compared informally to those from the remaining patients who do not receive M7824.

10.4.10

Halting Rules

If either of the below occurs, the Principal Investigator will halt accrual to the trial and will discuss with the NIH Intramural Institutional Review Board (IRB) whether any changes need to be made to the protocol.

- One occurrence of grade 5 toxicity by the NCI-CTCAE version 4.0 attributable to the treatment regimen.
- Two occurrences of grade 4 toxicity by the NCI-CTCAE version 4.0 attributable to the treatment regimen.
- More than two episodes of grade 3 colitis

This will apply to both cohorts—the phase I lead-in cohort and the main cohort of biochemical recurrence.

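### Section 10.2 sets the six M7824 recipients aside with no endpoint or time limit, so the 4-month immune test and the early PSA-slope test may use about 25 men when up to about 31 could contribute

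*Combined protocol and SAP*

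**What the plan says.** Section 2.3.1 describes Arm 2 as "Surveillance followed by Prostvac + CV301 then Prostvac + CV301 + MSB0011359C" and Arm 3 as "Surveillance as needed followed by Prostvac + CV301". Section 3.1 gives one vaccine schedule for the cohort and places M7824 in Arm 2 "starting after 4 months of concurrent Prostvac and CV301".

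The statistical sections then handle the M7824 recipients in several ways:

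- **10.2 (sample size):** "the initial 6 participants who received M7824 will be evaluated separately in exploratory fashion and will not be included among the 25 main participants". No endpoint or time window is attached.
- **10.3 (populations):** the only defined analysis set asks for at least one dose of the two vaccines and the checkpoint inhibitor.
- **10.4.2 (primary analysis):** "This primary analysis will not include the 6 patients who received M7824 before it was removed from future use in this study".
- **10.4.3 (PSA kinetics):** slopes after the vaccines, alone or with the checkpoint inhibitor, are tested against pre-vaccine slopes with a paired test at two-sided 0.05. No number of men is given.
- **10.4.9 (immune changes):** "The changes in the immune parameters after treatment with 2 vaccines for 4 months will be determined and tested for statistical significance", again with a paired test at two-sided 0.05 and no stated population. The same section has the PSA response of the M7824 recipients described and informally compared. The matching exploratory objective in 1.1.3 also concerns only their PSA decline.

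**The concern.** The 4-month immune question ends, by its own definition, before any M7824 is given. A PSA slope taken in the early vaccine months ends there too. Up to that point the two arms have had the same vaccines, so M7824 is no reason to leave Arm 2 out of these two tests. It is a good reason to leave Arm 2 out of the response analysis, where PSA is followed through the M7824 months.

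The sentence in 10.2 does not make that distinction. An analyst who follows it would drop the six men everywhere. At stake is some precision in small within-man tests. The analysis set is also left open for a family of immune tests that 10.4.9 already says will be numerous and unadjusted, and such a set is better fixed before the data are examined.

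**Working it through.** **Step 1. The plan's own figures.** Section 10.2 tests 15% against 35% with 25 men, "using an exact binomial test with a 0.10 one-sided significance level". The smallest cut-off with exact alpha at or below 0.10 is 7 of 25: alpha 0.0695, power 0.827 (stated 82%). The one-sided 90% bounds for 7/25 are 16.3% and 42.6%, as stated. Fisher's exact test of 35% in 25 against 10% in 36, one-sided 0.10, has power 0.814 (stated 81%). All reproduce. They are the only calculations to which the plan attaches the number 25, and neither is the immune test or the slope test.

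**Step 2. Who would be in the 4-month immune test?**

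| Text followed | Men included |
|---|---|
| 10.2, read without limit | about 25 (Arm 3) |
| 10.4.2, exclusion confined to the primary analysis | up to about 25 + 6 = 31 |
| 10.3, read literally | about 6 (Arm 2 only) |

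For the slope test, 10.4.3 leans towards including Arm 2. It plans slopes with the checkpoint inhibitor and keeps the lead-in men out of PSA analyses, so only Arm 2 can supply them. No section settles the choice for either test.

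**Step 3. What the six men add.** The documents give no effect size or standard deviation for these tests, so the standardised paired change d (mean change divided by the SD of the changes) is assumed, from 0.3 to 0.8. For a paired t-test at two-sided 0.05,

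power = P(|T| > t(0.975, n−1)), with T noncentral t on n−1 df and noncentrality d√n.

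For example, at d = 0.4 the noncentrality is 0.4 × √25 = 2.00 against 0.4 × √31 = 2.23.

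| d (assumed) | Power, n = 25 | Power, n = 31 |
|---|---|---|
| 0.3 | 0.30 | 0.37 |
| 0.4 | 0.48 | 0.58 |
| 0.5 | 0.67 | 0.77 |
| 0.6 | 0.82 | 0.90 |
| 0.7 | 0.92 | 0.97 |
| 0.8 | 0.97 | 0.99 |

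- Change detectable with 80% power: 0.58 SD with 25, 0.52 SD with 31.
- 95% interval half-width, t(0.975, n−1)/√n: 0.413 SD with 25, 0.367 SD with 31. The ratio is 0.367/0.413 = 0.889, so the interval is about 11% narrower.
- Extra men: 6/25 = 24%.

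**Step 4. What these figures take for granted.**

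- They need 31 complete pairs. Twenty-five is a target, and the number of Arm 2 men with paired samples is not reported.
- Section 12.4.1 lists a research draw at the start of cycle 5. The calendar in 18.1, as extracted, shows none at that visit; the table may be broken, so this should be confirmed.
- The six are defined by having received M7824, so they are men who stayed on treatment long enough to reach it. Adding only them would select on a later event. Arm 2 men who started vaccines but never reached M7824 belong in the pooled set too, and their number is not given.

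**The case against.** The strongest reply is that nothing in the plan excludes Arm 2 from these tests. The sentence in 10.2 stands under sample size; 10.4.2 ties the exclusion to the primary analysis; 1.1.3 and 10.4.9 confine the separate handling to PSA decline; and 10.3 and 10.4.3 point towards including Arm 2. This stands as far as it goes. A reader might infer that the immune and slope tests will be run on 25 men, but the documents do not say so. They leave the set open, and one natural reading of 10.2 gives 25.

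Three other stronger readings also fail:

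- **That the arms were treated exactly alike to month 4.** This is true of the vaccines only. Surveillance was a fixed part of Arm 2, is as needed in Arm 3, and was shortened by the 05/10/2023 amendment. That affects how the pre-vaccine slope is measured, so it bears on the slope test.
- **That 31 men have the data.** This is not shown, for the reasons in Step 4.
- **That a planned vaccine-only adverse-event analysis is being lost.** None is specified. Section 10.4.4 plans descriptive reporting with no cut at the first M7824 dose. A tabulation by period would be a useful addition.

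It can also be said that showing the six separately is a defensible preference in tests declared to be of secondary intent. That is fair, and it limits the importance of the point. It does not remove the need to say which set will be used.

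**Conclusion.** The point holds as a minor improvement. Arms 2 and 3 share the same vaccine regimen until M7824 starts, the exclusion in 10.2 is unlimited as worded, and five sections do not agree on who enters the 4-month immune test and the early slope test. Naming the set, and pooling data from before the first M7824 dose, would raise the number of men from about 25 to at most about 31. With complete pairs and assumed standardised changes of 0.4 to 0.5, that is worth about 10 points of power, and less at smaller or larger changes in the range examined. The interval narrows by about 11% whatever the change.

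Confidence is higher for the immune test than for the slope test, where the difference in surveillance length could matter. Leaving the six out of the primary response analysis is right and should stay.

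**What to change.** 1. **10.2:** limit the sentence on the six M7824 recipients to the PSA-response analyses. Section 10.4.2 already says this for the primary analysis and needs no edit.
2. **10.4.3 and 10.4.9:** state that tests using only data from before any M7824 dose (up to cycle 5 day 1) include all Cohort 2 men who received both vaccines, including Arm 2 men who never reached M7824. Show results pooled and by arm.
3. **10.4.3, slope test:** give the result with and without Arm 2, because the surveillance period behind the pre-vaccine slope differs between arms.
4. **10.3:** bring the population definition into line, so that it does not read as requiring the checkpoint inhibitor for these tests.
5. **10.4.4 (optional):** tabulate adverse events of the vaccine-only period in the same way.

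The cost is SAP wording, plus a check of which Arm 2 men have usable month-4 samples. No new collection is proposed. The downside is that two enrolment periods with different surveillance lengths are pooled; the by-arm display and the slope result without Arm 2 let a reader see whether that matters.
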